12.6 Statistical Analysis

12.6.1 General

Where appropriate, parameters will be analyzed using descriptive methods. Continuous parameters will be summarized using standard summary statistics as appropriate (n, mean, standard deviation, median, minimum and maximum). Summary statistics for categorical variables will include frequency counts and percentages. All subjects within the respective analysis set will be tabulated.

Graphical presentation of data may be performed.

12.6.2 Safety Analysis

Safety will be assessed by adverse events, laboratory tests, vital signs, physical examinations, ECGs, and liver and abdominal ultrasounds.

Adverse events will be tabulated by body system and preferred term. The number of entries, as well as the number of subjects will be reported. The nature, intensity, frequency, and relationship to IDN-6556 or placebo of adverse events will be described for all study subjects.

Results of laboratory tests, vital signs, physical examinations, and ECGs will be analyzed descriptively. Abnormal laboratory and ECG findings will be tabulated against appropriate cut-off points (e.g., $\geq 2 \times$ ULN) using frequency counts and percentages.

Furthermore, any prior and concomitant medication will be described.

Graphical presentation of results will be performed, where appropriate.

12.6.3 Efficacy Analysis

Primary Endpoint: Change from Baseline in Ishak Fibrosis Score at 2-years

The primary analysis of the primary endpoint will test the change in Ishak Fibrosis Scores at 24 months between the treatment groups in the FAS Population using ITT principles.

Subjects will be classified into one of the following 3 categories:

- Category 1. Regression at 24 months defined as a greater than or equal to a one point improvement in Ishak Fibrosis Score from Baseline.

Title: A Multicenter, Double-Blind, Randomized Trial of IDN-6556 in Subjects Who had Hepatitis C Virus (HCV) Reinfection and Liver Fibrosis or Cirrhosis following Orthotopic Liver Transplantation for Chronic HCV Infection and Who Subsequently Achieved a Sustained Virologic Response Following anti-HCV Therapy

- Category 2. Stable disease at 24 months defined as no change from Baseline in the Ishak Fibrosis Score from Baseline.
- Category 3. Progression at 24 months defined as a greater than or equal to a one point worsening from Baseline in the Ishak Fibrosis Score from Baseline or death/re-transplantation.

Changes in the Ishak Fibrosis Score at 24 months will be analyzed by a logistic regression model, appropriate for the analysis of ordinal categorical data, to derive the odds ratio and associated 95% confidence interval for IDN-6556 against placebo. The model will allow adjustment for the following variables:

- Baseline Ishak Fibrosis Score
- Immunosuppression regimen (classified into one of five groups: tacrolimus with/without steroids; cyclosporine with/without steroids; other)
- Age of the transplant donor
- Age of the recipient

Subgroup analyses of the model covariates, stated above, will also be conducted.

Shift tables of changes in Ishak Fibrosis Score over time will also be presented.

Secondary Endpoint

Estimates of the treatment effect of IDN-6556 versus placebo, and corresponding 95% confidence intervals of the modified Histological Activity Score will be conducted applying the suitable model for ordinal categorical data and detailed in the Statistical Analysis Plan. Shift tables showing changes over time will also be presented.

12.6.4 Interim Analysis

No formal interim analyses are planned for this exploratory study.

12.6.5 Handling of Missing Data

Methods for imputing missing data will be detailed within the Statistical Analysis Plan.

12.7 Analysis Plan

Prior to the analysis, a detailed SAP for the core study will be developed. This plan will be finalized prior to the database lock and/or study unblinding. It is intended that

Title: A Multicenter, Double-Blind, Randomized Trial of IDN-6556 in Subjects Who had Hepatitis C Virus (HCV) Reinfection and Liver Fibrosis or Cirrhosis following Orthotopic Liver Transplantation for Chronic HCV Infection and Who Subsequently Achieved a Sustained Virologic Response Following anti-HCV Therapy

the database will be locked once the last subject completes the 4 week follow-up visit.

A detailed analysis plan to determine the exposure effect relationship and the population pharmacokinetics will be developed separately. The results of the analysis will be generated as a stand-alone report.

12.8 Statistical Software

Analyses will be done using the validated statistical software of SAS® (version 9 or later).

12.9 Data Monitoring Committee (DMC)

An independent Data Monitoring Committee (DMC) is planned for this study. The DMC will review safety data at periodic intervals from this and all other IDN-6556 studies conducted by the Sponsor. Members of the DMC will not be allowed to participate as Investigators in this study and will not otherwise consult for the Sponsor.

A charter, which will include a detailed description of the scope and the extent of the DMC's responsibilities and procedures, will be implemented prior to any data review. DMC documents (charter, open and closed meeting minutes, etc.) will be considered part of the study documentation, but not part of this protocol. The DMC will review data within its general remit to oversee subject safety in the study, and provide recommendations and guidance to the Sponsor in accordance with the procedures stated in its charter.

Should the DMC make subject-safety-related recommendations which affect the conduct of this study, all Investigators, responsible IRB/IECs, and applicable regulatory agencies will be informed of any decisions made by the Sponsor in response to such DMC recommendations. The Investigators will inform the subjects of any such decisions, and the protocol and ICF will be revised, as appropriate.

13.0 ADVERSE EVENTS

13.1 Adverse Event Reporting Obligations

The Investigator is responsible for recording adverse events observed during the study. In addition, certain adverse events (as described in **Section 13.2.** below) are classified as "serious" and must be reported within 24 hours to Conatus or its designee.

Title: A Multicenter, Double-Blind, Randomized Trial of IDN-6556 in Subjects Who had Hepatitis C Virus (HCV) Reinfection and Liver Fibrosis or Cirrhosis following Orthotopic Liver Transplantation for Chronic HCV Infection and Who Subsequently Achieved a Sustained Virologic Response Following anti-HCV Therapy

In the case of certain adverse events, the Investigator and the Medical Monitor, after discussing the details of the adverse events, may decide to temporarily interrupt dosing, or permanently discontinue study drug treatment in a subset of subjects or in entirety.

13.2 Adverse Event Definitions

The following definitions of terms are guided by the International Conference on Harmonization and the U.S. Code of Federal Regulations [21 CFR 312.32] and are included herein.

An adverse event is any untoward medical occurrence associated with the use of a drug in humans, whether or not considered drug related.

Adverse events include, but are not limited to:

- Any symptom or condition not previously reported by the subject (medical history).
- An exacerbation of a pre-existing symptom or condition.
- A significant increase in frequency or intensity of a pre-existing episodic event or condition.
- A drug interaction.
- A condition first detected or diagnosed after study drug administration even though it may have been present prior to the start of the study.

An AE does **not** include:

- Medical or surgical procedures (e.g., surgery, endoscopy, tooth extraction, or blood transfusion); the condition that leads to the procedure is an adverse event (e.g., bleeding esophageal varices, dental caries).
- Overdose of either study drug or concurrent medication without any clinical signs or symptoms.

Suspected adverse reaction means any adverse event for which there is a reasonable possibility that the drug caused the adverse event. For the purposes of safety reporting, 'reasonable possibility' means there is evidence to suggest a causal relationship between the drug and the adverse event. A suspected adverse reaction implies a lesser degree of certainty about causality than adverse reaction, which means any adverse event caused by a drug.

Title: A Multicenter, Double-Blind, Randomized Trial of IDN-6556 in Subjects Who had Hepatitis C Virus (HCV) Reinfection and Liver Fibrosis or Cirrhosis following Orthotopic Liver Transplantation for Chronic HCV Infection and Who Subsequently Achieved a Sustained Virologic Response Following anti-HCV Therapy

An adverse reaction is any adverse event caused by a drug. Adverse reactions are a subset of all suspected adverse reactions for which there is reason to conclude that the drug caused the event.

An adverse event or suspected adverse reaction is considered “serious” if, in the view of either the Investigator or sponsor, it results in any of the following outcomes:

- Death
- A life-threatening adverse event
- Inpatient hospitalization or prolongation of existing hospitalization
- A persistent or significant incapacity or substantial disruption of the ability to conduct normal life functions
- A congenital anomaly/birth defect

Important medical events that may not result in death, be life-threatening, or require hospitalization may be considered serious when, based upon appropriate medical judgment, they may jeopardize the subject and may require medical or surgical intervention to prevent one of the outcomes listed in this definition. Examples of such medical events include allergic bronchospasm requiring intensive treatment in an emergency room or at home, blood dyscrasias or convulsions that do not result in inpatient hospitalization, or the development of drug dependency or drug abuse.

An adverse event or suspected adverse reaction is considered “life-threatening” if, in the view of either the Investigator or sponsor, its occurrence places the subject at immediate risk of death. It does not include an adverse event or suspected adverse reaction that, had it occurred in a more severe form, might have caused death.

An adverse event or suspected adverse reaction is considered ‘unexpected’ if it is not listed in the Investigator’s Brochure or is not listed at the specificity or severity that has been observed; or, if an Investigator’s Brochure is not required or available, is not consistent with the risk information described in the general investigational plan or elsewhere in the current application. For example, under this definition, hepatic necrosis would be unexpected (by virtue of greater severity) if the Investigator’s Brochure referred only to elevated hepatic enzymes or hepatitis. Similarly, cerebral thromboembolism and cerebral vasculitis would be unexpected (by virtue of greater specificity) if the Investigator’s Brochure listed only cerebral vascular accidents. ‘Unexpected,’ as used in this definition, also refers to adverse events or suspected adverse reactions that are mentioned in the Investigator’s Brochure as occurring with a class of drugs or as anticipated from the pharmacological properties of the drug, but are not specifically mentioned as occurring with the particular drug under investigation.

Title: A Multicenter, Double-Blind, Randomized Trial of IDN-6556 in Subjects Who had Hepatitis C Virus (HCV) Reinfection and Liver Fibrosis or Cirrhosis following Orthotopic Liver Transplantation for Chronic HCV Infection and Who Subsequently Achieved a Sustained Virologic Response Following anti-HCV Therapy

The Sponsor will determine if a suspected, unexpected serious adverse reaction (SUSAR) or SAE meets the criteria as being reportable as a 7-day or a 15-day safety report.

13.2.1 Anticipated Serious Adverse Events in HCV POLT SVR Subject Population

Given the chronic HCV subject population who underwent an orthotopic liver transplantation being studied in this protocol, serious adverse events are anticipated to occur, despite having achieved HCV viral clearance. As such, expected events in this patient population, with the exception of Immunologic and Infectious Disorders, if they become serious, will not be reported in an expedited manner because they may occur at some frequency, independent of drug exposure.

The Medical Monitor will review the subject data electronically via the EDC portal on an ongoing basis to ensure prompt review of protocol-specified SAEs. In addition, at minimum, quarterly outputs of all adverse events will be provided to the Medical Monitor to determine if any serious adverse events remain unreported and to establish routine monitoring of all adverse event data. The Medical Monitor will forward a summary of his/her review, if required by the DMC charter, to the DMC for additional safety oversight.

13.2.2 Pre-Treatment-Emergent Adverse Events

Conatus considers adverse events that occur between the time the subject signs the informed consent form for the study and the time when that subject is first administered the study drugs as “pre-treatment-emergent” events. Any pre-treatment-emergent event should not be recorded as an adverse event but should be recorded in the appropriate category of the subject’s medical history case report form.

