6.0 STUDY DESIGN

This is a double-blind, randomized, multicenter study involving subjects with chronic HCV who underwent liver transplantation; developed HCV-related liver fibrosis or cirrhosis; achieved a sustained virologic response (SVR) following anti-HCV therapy; and still show demonstrable fibrosis or cirrhosis on liver biopsy. Upon successful screening, subjects will be randomized to receive 25 mg BID of IDN-6556 or placebo in a 2:1 ratio.

[figure not shown]
The subjects will be stratified based on the stage of fibrosis or cirrhosis at Baseline:

1. Ishak F2
2. Ishak F3 – F5
3. Ishak 6

The study schema is outlined in Figure 6.1.

Title: A Multicenter, Double-Blind, Randomized Trial of IDN-6556 in Subjects Who had Hepatitis C Virus (HCV) Reinfection and Liver Fibrosis or Cirrhosis following Orthotopic Liver Transplantation for Chronic HCV Infection and Who Subsequently Achieved a Sustained Virologic Response Following anti-HCV Therapy

Figure 6.1 Study Schema

*A biopsy must be conducted if previous biopsy (bx) was >3 months prior to Day 1 or if tissue is not available.

Appendix I, the Schedule of Events Table*, indicates which procedures and evaluations will be performed throughout the study. An overview of key events is described below.

Screening Phase (Week -6 to Day 0): Subjects will sign an informed consent form (ICF) before any study-related procedures are performed. Subjects will be screened to determine their eligibility. Medical history and medication record (prior and concomitant medications) will be obtained for all subjects. A physical examination and a series of laboratory and diagnostic tests will be performed as described in the Schedule of Events. After confirming initial eligibility criteria, availability of prior liver biopsy will be assessed and a liver biopsy conducted if needed. The liver biopsy slides must be submitted to the central histopathologist who will confirm subject's eligibility prior to randomization.

* If any discrepancies should be found between the text of the protocol and the Schedule of Events Table, the table will predominate.

Title: A Multicenter, Double-Blind, Randomized Trial of IDN-6556 in Subjects Who had Hepatitis C Virus (HCV) Reinfection and Liver Fibrosis or Cirrhosis following Orthotopic Liver Transplantation for Chronic HCV Infection and Who Subsequently Achieved a Sustained Virologic Response Following anti-HCV Therapy

Double-Blind Phase (Month 0/Day 1 through to Month 24):

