7.0 STUDY POPULATION

Approximately 60 subjects who underwent orthotopic liver transplantation for chronic HCV, developed HCV-related liver fibrosis or cirrhosis, achieved a sustained virologic response with anti-viral treatment, and still have demonstrable fibrosis or cirrhosis on liver histology will be enrolled. Up to 15 subjects with an Ishak score of F6 can be enrolled.

Table 7.1 Treatment Arm Allocation

| Treatment Arm | N |
|--------------------|----|
| IDN-6556 25 mg BID | 40 |
| Placebo BID | 20 |
| TOTAL | 60 |

Subjects will be enrolled at approximately 35 clinical sites in the US. Expected duration of subject participation is as follows:

Title: A Multicenter, Double-Blind, Randomized Trial of IDN-6556 in Subjects Who had Hepatitis C Virus (HCV) Reinfection and Liver Fibrosis or Cirrhosis following Orthotopic Liver Transplantation for Chronic HCV Infection and Who Subsequently Achieved a Sustained Virologic Response Following anti-HCV Therapy

Table 7.2 Duration of Subject Participation

| | |
|--|---|
| Time expected for all subjects to be enrolled: | Approximately 12 months |
| Duration of individual subject participation: | Approximately 2.2 years (6 weeks Screening, 2 years treatment, and 4 weeks for follow-up) |

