8.0 STUDY ASSESSMENTS AND CONDUCT

8.1 Efficacy and Safety Assessments

8.1.1 Liver Biopsy

A screening liver biopsy must be performed prior to randomization if the prior biopsy was done more than 3 months prior to Day 1, or if tissue from the previous biopsy is not available. Ten (10) unstained liver biopsy sections, cut 4-microns-thick, must be submitted to the central histopathologist who will confirm subject's eligibility prior to randomization. Generally, the liver biopsy should be the last assessment performed during the Screening Phase prior to randomization and should only be performed in subjects who fulfill all other inclusion criteria.

After randomization, yearly (12 months \pm 42 day window) liver biopsies will be performed during the Double-Blind Phase of the study. In the event that a subject is withdrawn from the study prior to the 24 Month visit. The subject will be contacted and asked to sign a separate consent to return for the Month 24 liver biopsy. If premature discontinuation is within approximately 42 days of the originally scheduled Month 24 visit, the liver biopsy may be performed at the time of premature discontinuation. All reasonable attempts should be made to continue to follow the subject for the duration of the study follow-up period.

For all liver biopsies conducted during the Double-Blind Phase, 10 unstained sections, cut 4-microns-thick, must be available for analysis by the central histopathologist. In addition, all liver biopsies performed during the study should be of adequate quality to enable morphometric quantification of fibrosis and smooth muscle actin as well as meaningful interpretation of the histology by the central histopathologist.

Lastly, all liver biopsies taken during the course of the study, regardless of the indication (i.e., both protocol-defined and those performed for other clinical indications) must be assessed at the local institution and forwarded to the central histopathologist for assessment as well as being assessed at the local institution. In the event of any discrepancy between the local and central histopathology reports, the latter shall prevail.

Additional liver biopsies should be performed for subjects who show signs and symptoms of clinical worsening. Criteria for additional liver biopsy include:

- If the ALT at Baseline is \leq 60 IU/L and it is raised to \geq 3X ULN on two separate occasions separated by at least one week

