13.5 Recording and Reporting Adverse Events

13.5.1 Recording Adverse Events

All adverse events will be recorded in the appropriate section of the case report form. Subjects withdrawn from the study due to adverse events will be followed by the Investigator until the outcome is determined and, when appropriate, additional written reports and documentation will be provided. The Investigator should attempt, if possible, to establish a diagnosis based on the presenting signs and symptoms.

If the adverse event meets the definition of a serious adverse event, or if the Investigator becomes aware of an unexpected adverse event that places the subject at risk or a pregnancy at any time after the study drug administration up to the end of the study follow-up period, the event must be documented and reported as described in **Section 13.5.2**.

Title: A Multicenter, Double-Blind, Randomized Trial of IDN-6556 in Subjects Who had Hepatitis C Virus (HCV) Reinfection and Liver Fibrosis or Cirrhosis following Orthotopic Liver Transplantation for Chronic HCV Infection and Who Subsequently Achieved a Sustained Virologic Response Following anti-HCV Therapy

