APPENDIX I: SCHEDULE OF EVENTS

| | STUDY VISITS ^A | | | | | | | | | | | | |
|---|---------------------------------------|--------------------|-----------|--------|--------|----------------|--------|----------------|---------|----------------|---------|----------------|------------------------------|
| | Screening Phase (Week -6 to Day 0) | Double-Label Phase | | | | | | | | | | | Follow-Up Phase |
| | | M0/ Day 1 | Day 14 | M 1 | M 3 | M 6 | M 9 | M 12 | M 15 | M 18 | M 21 | M24/ ET/EOT | M25/ 4 Wks post ET/EOT |
| Study Procedures | | | | | | | | | | | | | |
| Informed Consent | X | | | | | | | | | | | | |
| Eligibility Criteria | X | | | | | | | | | | | | |
| Medical and Surgical History | X | | | | | | | | | | | | |
| Medication/Therapy Record | X | X | X | X | X | X | X | X | X | X | X | X | X |
| Vital Signs | X | X | X | X | X | X | X | X | X | X | X | X | X |
| Physical Examination (including weight, height at screening only) | X | | | | | | | X | | | | X | X |
| Chest X-ray | X | | | | | | | | | | | | |
| 12 Lead ECG | X | | | | | | | X | | | | X | |
| Liver and Abdominal Ultrasound | X ^B | | | | | X ^C | | X ^C | | X ^C | | X | |
| Liver Biopsy | X ^D | | | | | X ^E | | X ^F | | X ^E | | X ^F | |
| Transient Elastography (at select centers only) | X | | | | | X | | X | | X | | X | |
| Study Drug Administration/Dispense Study Drug | | X | X | X | X | X | X | X | X | X | X | | |
| Compliance Assessment (Capsule Count) | | | X | X | X | X | X | X | X | X | X | X | |
| Adverse Event Assessment | | X | X | X | X | X | X | X | X | X | X | X | X |
| Clinical Laboratory Evaluations | | | | | | | | | | | | | |
| Hematology | X | X | | X | X | X | X | X | X | X | X | X | X |
| Chemistry | X | X | X | X | X | X | X | X | X | X | X | X | X |
| Coagulation | X | X | | X | | X | | X | | X | | X | X |
| Urinalysis | X | X | | | | X | | X | | X | | X | X |
| Immunosuppressant Concentration Monitoring | | X | X | | | | | | | | | | |

Title: A Multicenter, Double-Blind, Randomized Trial of IDN-6556 in Subjects Who had Hepatitis C Virus (HCV) Reinfection and Liver Fibrosis or Cirrhosis following Orthotopic Liver Transplantation for Chronic HCV Infection and Who Subsequently Achieved a Sustained Virologic Response Following anti-HCV Therapy

| | STUDY VISITS ^A | | | | | | | | | | | | |

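### Complications of a protocol-required screening biopsy go to the medical history form, so they miss the adverse event data and it is unclear whether serious ones must be reported

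*Protocol*

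**What the plan says.** Protocol 13.2.2 defines a pre-treatment window covering "adverse events that occur between the time the subject signs the informed consent form" and first administration of study drug. Its rule for that window is "Any pre-treatment-emergent event should not be recorded as an adverse event"; instead, the event "should be recorded in the appropriate category of the subject’s medical history case report form". The section has no exception for serious events or for events caused by a study procedure.

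Protocol 8.1.1 places an invasive study procedure inside that window for some subjects: "A screening liver biopsy must be performed prior to randomization if the prior biopsy was done more than 3 months prior to Day 1". The same applies if tissue from the earlier biopsy cannot be obtained. Section 6.0 fixes the order of events: "Subjects will sign an informed consent form (ICF) before any study-related procedures are performed". Table 7.2 gives the time split as "6 weeks Screening, 2 years treatment, and 4 weeks for follow-up", so the window can last up to six weeks.

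Protocol 13.5.1 sends serious events, and certain other events, to the reporting procedure in 13.5.2, and uses the phrase "at any time after the study drug administration up to the end of the study follow-up period". Sections 13.5.2 (24-hour report to the sponsor) and 13.9 (ethics committee notice) cover all serious adverse events and state no start date.

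**The concern.** The protocol asks some subjects to have a liver biopsy for the purposes of the study, then classes whatever harm follows as background history if it happens before the first capsule. In a dosed subject still under follow-up, the same bleed after the Month 12 biopsy would be an adverse event and, if serious, would clearly be due for a 24-hour report. The harm and its cause are the same; only the date relative to first dose differs.

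What is at stake is participant protection and a complete account of what the study's own procedures cost its subjects. The efficacy result is not at stake. Subjects who have the biopsy and then fail screening are the most exposed to the gap, because they never reach any point at which adverse events are collected.

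**Working it through.** The documents give no figure that depends on this rule, so there is nothing to recompute. The check follows an event through the text.

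1. **Does the screening biopsy fall in the window?** Consent precedes all study procedures (6.0), and a biopsy required by 8.1.1 must come before randomization, hence before first dose. A biopsy done for the study is therefore inside the 13.2.2 window. A routine-care biopsy taken before consent is outside it.

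2. **Is the event an adverse event on the form?** Under 13.2.2, no. Appendix I agrees: the row reads "Adverse Event Assessment | | X | X", with the Screening cell blank and the first mark at Month 0/Day 1. By the footnote in 6.0 the table overrides the text, so nothing elsewhere in the protocol restores screening collection.

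3. **Is the alternative form suited to it?** Appendix I schedules medical history at Screening only, and 8.1.1 says the biopsy should generally be the last screening assessment. The form may already be complete when the complication occurs.

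4. **What does the event then miss?**
   - The quarterly outputs to the Medical Monitor in 13.2.1, which are outputs of adverse events.
   - Follow-up to resolution in 13.7, which is written for adverse events.
   - The treatment-emergent tables, because SAP 5.4.3 counts from the first dosing date.
   - For a subject never dosed, every SAP safety table, because the Safety Analysis Set in SAP 6 requires randomization and at least one dose.

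5. **Is a serious one reported within 24 hours?** Two readings are possible.
   - *Not reported.* Section 13.2.2 removes adverse event status, so the event cannot be a serious adverse event. The time phrase in 13.5.1 points the same way.
   - *Reported.* Sections 13.5.2 and 13.9 cover all serious adverse events without a start date, and 13.2.2 speaks only of recording. The time phrase in 13.5.1 may attach only to its later limbs (unexpected events that put the subject in danger, and pregnancies).

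   The first is the more natural reading, but the text does not settle it.

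6. **Could the existing route handle it?** Only in part. The initial report in 13.5.2 needs a subject number, but under 7.3 only qualified subjects receive one; others have a screening number. The scale in 13.4 rates relationship to IDN-6556 or placebo only, so harm from a procedure cannot be coded.

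**The case against.** The strongest case on the other side has four parts.

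- **The convention is deliberate and internally coherent.** Section 13.2 ties an adverse event to the use of a drug, and events before first dose cannot be drug effects. They are still recorded on a form, and they cannot distort the comparison between arms. All of this is correct. It explains the rule, but it leaves harm from a study procedure without a proper place in the safety data.

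- **Oversight may still see these events.** A reader might infer that the Data Monitoring Committee and ethics committees cannot see them. The documents do not support that. Section 12.9 gives the Data Monitoring Committee safety data under a charter that is not among the documents. Section 13.2.1 gives the Medical Monitor continuing access to subject data through the electronic capture portal, apart from the quarterly outputs. Section 14.1 requires at least yearly progress reports to the ethics committee and compliance with its local reporting rules. What remains is that the protocol does not assure such review.

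- **Serious-event reporting is not expressly switched off.** A reader might take 13.2.2 and 13.5.1 as barring it. As step 5 shows, 13.5.2 and 13.9 can be read the other way. What remains is an ambiguity in a safety duty, which itself needs correcting.

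- **Exposure is limited.** A reader might suppose that most of the 60 subjects, plus screen failures, are affected. The documents give no basis for that. The biopsy is conditional, and 8.1.1 reserves it for subjects who meet all other inclusion criteria. That largely confines exposed screen failures to those excluded on the biopsy result. This stands in full, and the number remains unknown.

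**Conclusion.** The recording gap is real and explicit. Complications of a required screening biopsy do not enter the adverse event data, the quarterly adverse event outputs or the SAP safety tables. Expedited reporting of serious ones, to the sponsor and to ethics committees, is at best unclear, and Data Monitoring Committee review is not assured.

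The size cannot be stated. The documents give neither the share of subjects who need a screening biopsy nor a complication rate. Subjects with an eligible recent biopsy and available tissue are unaffected.

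Two limits apply. The gap does not bias the between-arm comparison or the treatment-emergent tables, because the events precede first dose. The contrast with on-treatment biopsies holds for dosed subjects still under follow-up. A subject who has left the study and returns only for the Month 24 biopsy may fall under 13.8, which asks for notice of a serious event only if it is attributed to study drug.

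The conclusion rests on reading 13.2.2 as written, on consent preceding the study biopsy, and on no charter or site instruction outside these documents filling the gap. The change is worth making because it serves participant protection at little cost.

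**What to change.** Amending 13.2.2 alone would not be enough, because Appendix I overrides the text. The changes belong together:

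- **13.2.2:** from consent to first dose, record events attributed to a protocol-required procedure as non-treatment-emergent adverse events, and report serious ones under 13.5.2.
- **13.5.1:** align the time phrase so that serious procedure-related events from consent onward are clearly covered.
- **Appendix I:** add a Screening mark to the Adverse Event Assessment row.
- **13.4:** add an item for relationship to a study procedure.
- **13.5.2:** accept the screening number in place of the subject number for subjects never randomized.
- **SAP:** add one separate listing of these events on the Enrolled Set, which SAP 6 already defines as those who signed consent, so that screen failures are included. Leave the treatment-emergent definition in SAP 5.4.3 unchanged.

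The cost is a protocol amendment touching five places, one extra listing and a small amount of extra site recording. Efficacy analyses, sample size and treatment-emergent tables do not change.
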